Outpatient cardiology and internal medicine providers in the Yale health system will be selected for potential participation in the study based on the frequency with which they see patients who meet the inclusion criteria (must see at least 10 potentially eligible patients per week). They will be identified based on a retrospective review of clinical encounters that include patients at very high risk for ASCVD events based on clinical guidelines within Epic and approached for consent to participate in the study. Once consented, we will determine baseline prescribing patterns for lipid lowering therapy (over 3months) specifically looking at the proportion of very high risk ASCVD patients on high-intensity statin therapy, ezetimibe, or PCSK9 inhibitor as well as distribution of LDL-C. All physicians will then be randomized within Epic to either the intervention group or the control (usual care) group via a permutated block randomization scheme to ensure an equal number of providers in each study arm. Logic checks within the alerts ensure that once a provider is assigned to an arm, they remain in that arm for the remainder of the study. This will create 100 clusters (providers) to which eligible patient participants will be assigned upon their outpatient visit. In other words, any patient seen by a provider randomized to the intervention (alert) group will have an informational alert generated when their provider opens the order entry screen in the patient's medical record. On the contrary, any patient seen by a provider randomized to the control arm will not generate an alert and will receive usual care. Instead, a "silent alert" that simply registers the patient into the trial by the study team is generated. Because it is likely that providers may internalize the best practice metrics once repeatedly exposed to the alert, cluster randomization of patients at the level of the provider will ensure that providers consistently receive an alert or not, which will reduce contamination between study arms. It will also minimize the chance that providers get so accustomed to seeing an alert for hyperlipidemia that they will become less attentive to the condition in patients not generating an alert. Additional pre- and postintervention analyses in the control group, leveraging the three-month baseline period, can assess the level of contamination and the effect of secular trends towards better care over time.

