Once a patient is seen by an enrolled-provider, they will not generate further alerts. This ensures that the rare patient who is seen by two providers from different arms of the study cannot be enrolled twice.

Identification of patients to be involved in the study and generation of an alert (or not) will be performed entirely within the Epic medical records system based on inclusion and exclusion criteria outlined below. This will be done using a best-practice alert build developed by the data analytics team at Yale that will, upon opening the order entry screen in the patient's chart by a enrolled provider, examine the medical record to identify the patient as having very high risk for ASCVD (see ICD-10 codes below) as well as an LDL-C > 70mg/dL without a recent change in lipid lowering therapy (dose escalation or addition of new therapy). If these conditions are met, the patient will be included in the study and then depending on whether the provider is randomized to the alert or usual care arm, will determine whether an alert is shown upon entering the order screen within the medical record.

Providers in the intervention (alert) group will have an alert generated within the electronic medical record system for all patients who meet criteria. The alert will fire once per patient, during the patient's first eligible outpatient visit, when the provider opens the order entry screen in the patient's electronic medical record. This will maximize the chance that the alert appears at the most relevant place in the provider's workflow. There will be a 1-hour lockout feature such that a provider randomized to receiving alerts will not receive another alert within 1 hour but outside that window would receive another alert for the patient if they enter the order page of the record.

The alert will consist of a "pop-up" that notifies the physician that the patient is at very high risk for ASCVD events, displays the most recent cholesterol values and current lipid lowering therapy. In addition to noting that the provider should ensure adherence to both current lipid-lowering therapy and lifestyle modifications, a link to full treatment guidelines for hyperlipidemia is also provided and includes a continuing medical education (CME) option to obtain CME credits. An example of what this alert will look like is as follows:

) Patient May Need Lipid Me	dication Optimization		
Your patient has clinical ath	erosclerotic cardiovascular disease (/	SCVD)	

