Objectives and Endpoints: The objective of this study is to evaluate the efficacy of targeted electronic alerts to improve rates of best practices in the treatment of patients with hyperlipidemia who are seen by outpatient cardiology and internal medicine physicians. The primary outcome will be the proportion of patients who have intensification of their lipid lowering therapy (increase in statin dose or addition of ezetimibe or addition of a PCSK9 inhibitor) at 90-days. The secondary outcomes will be achieved LDL-C (fasting or non-fasting) at 6-months and rates of hospitalization for myocardial infarction, stroke, unstable angina, coronary or peripheral artery revascularization.

Consent and Survey distribution: Provider consent will be collected in one of several ways, and we are requesting a waiver of documentation of consent for providers in this study, as the study poses minimal risk. The first method for provider outreach and consent will be done through university email in which a link to the consent and provider survey will be provided. In this method, the consent and survey will be administered electronically via REDCap (Research Electronic Data Capture) and an electronic signature will be captured. This link to the consent form will be sent to all eligible providers that will direct them to our online consent form in REDCap for review and signature. If the provider consents, we will follow up and send a survey link that will direct them to the survey form in REDCap.

Should provider outreach via email prove difficult, we will use other means to contact eligible providers. The first will be via an Epic inbasket message, where the informed consent will be copied directly into the body of an Epic message that is then sent to the eligible provider. The provider can then read through the consent and reply back to the inbasket message with "Yes I do consent" or "No I do not consent", without requiring a signature on the consent document. This response will be document, and consented providers will then be sent further instructions and a link for the REDCap survey.

We will also contact providers via telephone, where study personnel will describe the study via phone, answer questions, and receive and document provider verbal consent. Consented providers will then be sent further instruction and a link for the REDCap survey.

If/when feasible, study coordinators will also conduct in-person recruitment to obtained signed consent.

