- Currently being seen as an outpatient of a cardiology or internal medicine practice associated with a teaching hospital within the Yale New Haven Health System (Yale New Haven Hospital, St. Raphael's Campus, Bridgeport Hospital and Greenwich Hospital). Clinics may be on site or a satellite office associated with the hospital.
- Very high risk for ASCVD defined as history of a major ASCVD event (at least one ICD-10 code below) AND most recent lipid profile with LDL-C > 70mg/dL with or without other high-risk features (diabetes, chronic kidney disease, or age > 65).

Exclusion Criteria

- Heart transplant
- Left Ventricular Assist Device
- Hospital inpatient status
- Pregnancy
- Have opted out of clinical research via MyChart

Providers must be practicing at an outpatient cardiology and internal medicine practices at or associated with one of the four teaching hospitals within the Yale New Haven Health System (located on site or at a satellite office) and will be selected for study participation based on the frequency with which they see patients who meet the above criteria, based on a retrospective review (must see a minimum of ten eligible patients per week).

Table outlining conditions that comprise the definition of a history of major ASCVD event (adapted from Colantonio LD et al. JACC 2019;74: 2496-2507).

Condition	Algorithm	List of diagnosis and procedure codes

History of myocardial infarction	 ≥1 overnight inpatient claim with a discharge diagnosis code for acute myocardial infarction in any discharge diagnosis position. ≥1 inpatient claim with a discharge diagnosis code for old myocardial infarction in any discharge diagnosis position. ≥2 outpatient claims with a diagnosis code for old myocardial infarction at least 30 days apart, but less than 365 days apart. 	Diagnosis codes for acute myocardial infarction: ICD9: 410.x0, 410.x1. ICD10: I21.x, I21.xx, I22.x. Diagnosis codes for old myocardial infarction: ICD9: 412. ICD10: I25.2.
Unstable angina	≥1 inpatient claim with a discharge diagnosis code for unstable angina in any discharge diagnosis position within past 12 months.	ICD9 diagnosis codes: 411.1, 411.81, 411.89. ICD10 diagnosis codes: I20.0, I24, I24.0, I24.8, I24.9, I25.110, I25.700, I25.710, I25.720, I25.730, I25.750, I25.760, I25.790.

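### The three-month provider baseline records who is on therapy, not 90-day intensification in trial-eligible patients, so it is a weak check on contamination and secular trend

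*Combined protocol and SAP*

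**What the plan says.** All of this is in the combined protocol and SAP, Section I.

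- **Baseline (Research Plan).** Between provider consent and randomization, three months of prescribing are to be summarised, "specifically looking at the proportion of very high risk ASCVD patients on high-intensity statin therapy, ezetimibe, or PCSK9 inhibitor". LDL-C values are to be tabulated too.
- **Intended use (Research Plan).** "Additional pre- and postintervention analyses in the control group, leveraging the three-month baseline period, can assess the level of contamination"; the same sentence adds the effect of secular trends.
- **Trial cohort (Research Plan, alert build).** When an enrolled provider opens order entry, the build looks for a very high risk diagnosis "as well as an LDL-C > 70mg/dL without a recent change in lipid lowering therapy (dose escalation or addition of new therapy"). The patient enters at the first eligible visit. In the control arm a silent alert registers the patient.
- **Inclusion criteria (item 4).** Very high risk is defined there as a major ASCVD event "AND most recent lipid profile with LDL-C > 70mg/dL with or without other high-risk features". The no-recent-change condition is not in this list.
- **Primary outcome (Objectives and Endpoints).** "intensification of their lipid lowering therapy (increase in statin dose or addition of ezetimibe or addition of a PCSK9 inhibitor) at 90-days".
- **Primary analysis (item 9, Statistical Considerations).** Logistic regression on randomization status, clustered by provider, with no baseline term.

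**The concern.** A pre/post check works when the same quantity is measured on the same kind of patient in both periods. Here the pre-period quantity is the share of patients already on a drug. What contamination or a secular trend would move is the rate at which control providers step up therapy in eligible patients. A share on therapy reflects years of past prescribing, stopping and patient turnover, and it can stay nearly flat while the rate of intensification changes a good deal.

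What is at stake is interpretation. If the two arms end up close, this is the analysis the plan offers for asking whether control providers had improved as well. The baseline as described would help little with that question. It also leaves the trial without a pre-trial 90-day intensification rate in its own eligible population. The planning rate of 5% in item 9 does not fill that gap, because it is labelled as the current ezetimibe rate.

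**Working it through.** **Step 1. Baseline against trial, item by item.**

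| | Three-month baseline | Trial |
|---|---|---|
| Quantity | Share on listed therapy (prevalence) | Intensification by 90 days (incidence) |
| LDL-C above 70 mg/dL | Not stated; may be implied by item 4 | Required |
| No recent therapy change | Not stated | Required by the alert build |
| Index visit | Not stated | First eligible visit |
| Exclusions | Not stated | Listed in item 4 |

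The LDL-C row is ambiguous. Item 4 writes the LDL-C limit into its definition of very high risk, but the Research Plan lists it as a separate condition, and the baseline is to tabulate the LDL-C distribution. The quantity, no-recent-change and index-visit rows differ on either reading.

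**Step 2. Is the baseline measure repeated later?** The outcomes listed are 90-day intensification, achieved LDL-C at six months, the proportions below 70 and below 55 mg/dL, long-term events, and provider measures. None is the share of very high risk patients on each therapy. The LDL-C outcomes come closest to a match, but they are taken six months on, in patients selected for LDL-C above 70 mg/dL.

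**Step 3. A yardstick for drift.** Item 9 gives 80% power for 5% against 9.3% with 50 providers per arm, 25 patients each and an ICC of 0.05.

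- Design effect: 1 + (25 − 1) × 0.05 = 2.2.
- Effective size per arm: 1250 / 2.2 = 568.2.
- Power, pooled two-proportion test, two-sided 0.05 (the level is not stated and is assumed): 80.4%. The plan's figure reproduces.

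A control-arm drift of 9.3 − 5 = 4.3 points would therefore be as large as the effect the trial is sized to detect, and a useful check should register it.

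**Step 4. How far would the baseline measure move?** Let *s* be the share of the baseline population that meets the trial's eligibility rule, and *f* the share of intensifications that change a patient's on/off status. Assume that status does not change in the others. Over one 90-day period the extra movement is

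extra change in on-therapy share = *s* × *f* × 4.3 points.

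The documents give neither *s* nor *f*. The Background cites registries in which fewer than 35% reach LDL-C below 70 mg/dL, so *s* = 0.65 is used as one value; the no-recent-change rule would lower it. *s* = 1 is the limit in which the two populations coincide.

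| *s* | *f* = 0 | *f* = 0.5 | *f* = 1 |
|---|---|---|---|
| 0.65 | 0 | 1.4 | 2.8 |
| 1.00 | 0 | 2.15 | 4.3 |

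Adding ezetimibe in a patient already on a high-intensity statin meets the primary endpoint but has *f* = 0 if the three drugs are counted as one composite. If three separate proportions are meant, that addition does show in the ezetimibe figure. A statin dose increase that does not cross into high intensity still shows nowhere.

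**The case against.** The strongest reply is that the plan does not commit to comparing baseline prevalence with 90-day intensification. It names a period, not an outcome, and says only that such analyses can be done. A comparison of on-therapy shares before and after, in control providers' very high risk patients, would be like for like. This stands: a reader might infer that the planned comparison must show a difference even if prescribing never changes, and the documents do not support that. What remains is that no post-period on-therapy measure is described and that, even if one were added, step 4 shows it can respond poorly.

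A reader might also infer that a three-month window cannot hold a 90-day endpoint and would lose about half the events. That does not follow either. The baseline is a prevalence and needs no follow-up. If intensification were measured instead, outcomes come from the chart, and follow-up could run past the end of the window. The plan describes no incidence cut off at the window's close.

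The baseline description is one sentence, and its silence on the eligibility rule is not proof that the rule will not be applied. The LDL-C limit may be implied. This too stands, so the point is that the plan does not state a matched baseline, not that it rules one out.

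Finally, the pre/post work is supplementary and confined to the control arm. The randomized comparison has its own concurrent control rate.

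**Conclusion.** The point holds in a limited form. The baseline as written is not the trial's endpoint in the trial's eligible cohort, and no matching measure is planned for the trial period. The pre/post analysis is therefore a weak check on contamination or secular trend.

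The size is illustrative only. A control-arm drift equal to the trial's detectable difference, 4.3 points, would move a composite on-therapy share by 0 to 4.3 points depending on *s* and *f*. The result rests on those two assumptions and on the planning rates of 5% and 9.3%. The mismatch in step 1 needs none of them.

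The validity and power of the primary analysis are not affected. This is an inexpensive improvement to a supplementary analysis.

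**What to change.** In the Research Plan, where the baseline is described, replace the pre-period with a matched cohort:

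- Run the alert's eligibility logic retrospectively on each consented provider's visits in a three-month window. Use the same exclusions and the same look-back for a recent therapy change as the live build; the plan does not give the length of that look-back and should state it.
- Take each patient's first eligible visit as the index visit and compute the 90-day intensification endpoint as in the trial.
- End the window at least 90 days before go-live so that follow-up is complete by then. Preferably it should also be complete before consent-related education, since provider outreach reviews the guidelines and education is part of the consent process.
- Name this cohort and this endpoint as the pre-period for the control-group pre/post analysis, with clustering by provider as in the primary analysis.
- Keep the on-therapy proportions and the LDL-C distribution as description.

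The cost is one extra EHR query with logic already built for the alert; no patient contact or new data collection is needed. The drawback is a pre-period about three months older, which lengthens the gap over which secular change accrues. A matched before/after comparison in the control arm will still show contamination and secular change together, and the report should say so. Merely naming an on-therapy outcome and repeating it in both periods would avoid the older window, but it would keep the poor response shown in step 4.

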atorvastatin (LI In order to improve the care In addition to ensuring adhe whether any of the following Add Ezetemibe Add PCSK9i This patient is part of a rand substitute for clinical judgme may not be listed here due clinical decisions. There are guidelines, click here.	e of patients at high risk for adverse C prence to current lipid lowering medica g are appropriate for your patient: domized clinical trial. The guideline-re ent and individual-patient-centered de to patient allergy or contraindication F e clinical reasons why these recomme	tion and continued lifestyle modification, commended treatment for hyperlipidemia cision making. Evidenced-based therapie ease consult with the attending provider adations may not apply to your patient. Fo	please consider in the alert IS NOT s include those tha before making any

At the bottom of the alert, there will be an option to "dismiss" or accept the alert. If a provider chooses to dismiss the alert, a drop-down menu will appear that will display options for the reason for dismissing the alert from which the provider can select, including that the alert was not germane to the patient, or that another clinical reason precludes them from intensifying the patient's lipid-lowering therapy. Providers can choose to accept or dismiss the alert and act accordingly based on their own clinical judgement. They can decide at their own discretion whether or not following the guidelines included in the alert is appropriate or not for their patient and are not obligated or required to take any specific action relating to this alert. This alert and its associated guidelines are not a substitute for a clinical consultation and recommendation.

Engaging Providers: The study team will be blinded to the treatment assignment until the end of the trial period. We will engage in pre-trial outreach to all eligible providers, informing them of the background and rationale of the study, reviewing evidence-based guidelines, and outlining the randomized nature of the study and the alert intervention. We will additionally inform them that limited data is being collected regarding provider behavior. However, we will also make it clear that such data will not be linked to individual clinicians and no clinicians will be linked to any specific outcome.

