- 1. Targeted Enrollment: Give the number of subjects: 100 providers, 2500 patients
 - a. Targeted for enrollment at Yale for this protocol: 100 providers, 2500 patients
 - b. If this is a multi-site study, give the total number of subjects targeted across all sites: N/A

2. Indicate recruitment methods below. Attach copies of any recruitment materials that will be used.

□ Flyers	Internet/web postings	🗆 Radio
□ Posters	Mass email solicitation (providers)	⊠ Telephone
	only)	(providers only)
Letter	Departmental/Center website	Television
⊠ Medical record review*	Departmental/Center research boards	□ Newspaper
Departmental/Center newsletters	□ Web-based clinical trial registries	□ Clinicaltrails.gov
YCCI Recruitment database	Social Media (Twitter/Facebook):	
□ Other:		

* Requests for medical records should be made through JDAT as described at

http://medicine.yale.edu/ycci/oncore/availableservices/datarequests/datarequests.aspx

3. Recruitment Procedures:

- a. Describe how potential subjects will be identified. Patient subjects will be identified using an electronic algorithm that interfaces with Epic databases. Provider subjects will be identified using retrospective review and based on frequency with which providers see hyperlipidemia patients.
- b. Describe how potential subjects are contacted. There will be no formal contact between patient subjects and study personnel and we will be requesting a waiver of informed consent for patients. Providers will be contacted and asked to consent for study participation via one of the methods described above (via email, Epic in basket messaging, and telephone). Pre-trial education during the consent process will be performed, as well periodic outreach to all participating providers. Who is recruiting potential subjects? For patients, this will be done electronically via the electronic health record. Patients will be identified if they are seen in outpatient general medicine or cardiology clinic and meet the inclusion and exclusion criteria stated above. Providers will be recruited and contacted by study coordinators and the principle investigator.

4. Assessment of Current Health Provider Relationship for HIPAA Consideration:

Does the Investigator or any member of the research team have a direct existing clinical relationship with any potential subject?

- □Yes, all subjects
- \Box Yes, some of the subjects

⊠No

If yes, describe the nature of this relationship. Write here

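### The control-group before/after analysis cannot measure contamination or secular trend, because it estimates only their sum

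*Combined protocol and SAP*

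**What the plan says.** The claim is in Section I, Research Plan, in the paragraph on provider selection and cluster randomization. After giving contamination as a reason for randomizing providers rather than patients, the plan adds that before/after comparisons among control providers, "leveraging the three-month baseline period, can assess the level of contamination and the effect of secular trends towards better care over time".

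The same paragraph describes the baseline. Prescribing patterns are determined over three months once providers have consented, looking at "the proportion of very high risk ASCVD patients on high-intensity statin therapy, ezetimibe, or PCSK9 inhibitor as well as distribution of LDL-C". Randomization follows. For the control condition, "any patient seen by a provider randomized to the control arm will not generate an alert and will receive usual care".

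Two other places bear on what can move the control arm. Under Engaging Providers: "We will engage in pre-trial outreach to all eligible providers, informing them of the background and rationale of the study, reviewing evidence-based guidelines". Under Recruitment Procedures (Section III, item 3): "Pre-trial education during the consent process will be performed, as well periodic outreach to all participating providers".

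Statistical Considerations (Section I, item 9) does not mention the control-group analysis. It gives a logistic regression on randomization status clustered by provider, with no period or baseline term. No model, outcome, time unit or comparison group is given anywhere for the pre/post analysis.

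**The concern.** The plan promises two quantities from a contrast that yields one. If control providers intensify therapy more often during the trial than at baseline, the cause could be better care everywhere, ideas passed on by alert-arm colleagues, or the study's own outreach. All three push the same number in the same direction.

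This matters because the explanations imply different things about the alert. A secular trend that reaches both arms leaves the between-arm difference intact. Contamination shrinks it. Providers are randomized individually, so alert and control providers may work in the same practice. If the trial ends with a small or null difference, someone will want to know whether contamination explains it, and this is the only analysis in the plan that claims to say.

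**Working it through.** **1. The plan's own figure.** Inputs from Statistical Considerations: 50 providers per arm, 25 patients each, ICC 0.05, 5% against 9.3%. Two-sided alpha of 0.05 is assumed, because none is stated.

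- Design effect = 1 + (25 − 1) × 0.05 = 2.2.
- Effective patients per arm = 1250 / 2.2 = 568.
- Power = 80.4%, which reproduces the stated 80%.

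This does not test the claim, but it supplies the scale: a design difference of 9.3 − 5.0 = 4.3 points.

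**2. What the contrast identifies.** Let B be the baseline rate, S the secular trend, C contamination and A the alert effect, all additive. Leave outreach aside for now.

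- Control, before: B
- Control, after: B + S + C
- Alert, after: B + S + A

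Control providers alone give two equations in three unknowns (rank 2 of 3), so only S + C is estimable. Adding the alert arm's before and after data gives rank 3 for four unknowns, which still does not separate S from C. A concurrent group untouched by the trial (after: B + S) gives rank 4 of 4, provided that it shares the same trend.

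Now let O be the effect of outreach and study awareness that arises after baseline in enrolled providers. The control change becomes S + C + O. Even against the untouched group, the difference is C + O, not C.

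**3. Could a projected baseline slope separate them?** Take three monthly baseline points (months 1 to 3, mean 2) and nine trial months (4 to 12, mean 8). Assume 1250 / 9 = 139 control patients per month, also at baseline, a 5% rate and no clustering.

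- Monthly SE = √(0.05 × 0.95 / 139) = 1.85 points.
- Multiplier = √(1/3 + (8 − 2)²/2 + 1/9) = 4.29.
- SE of the contamination estimate = 1.85 × 4.29 = 7.9 points.

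That exceeds the 4.3-point design difference, and clustering would generally add to it.

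**4. What the ambiguity could amount to.** All control rates after baseline below are assumed. The 5% start is also an assumption, since the plan calls it the current ezetimibe rate and not an intensification rate. The alert arm is held at 9.3%.

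| Control after | Observed difference | Uncontaminated difference if the rise is all trend | Uncontaminated difference if the rise is all contamination | Power for the observed difference |
|---|---|---|---|---|
| 6% | 3.3 | 3.3 | 4.3 | 55% |
| 7% | 2.3 | 2.3 | 4.3 | 29% |
| 8% | 1.3 | 1.3 | 4.3 | 12% |

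In each row the pre/post analysis returns the same number (a rise of 1, 2 or 3 points) under both explanations.

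**5. Scale.** The baseline measures are the proportion of patients on each therapy and the LDL-C distribution. The primary endpoint is a new intensification within 90 days, in patients above the LDL-C threshold without a recent therapy change. A change from the first measure to the second is not a before/after change in the endpoint.

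**The case against.** Four points can be made for the plan.

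- **The sentence is optional and carries no decision.** This stands. A reader might infer that the plan depends on this analysis to interpret a small between-arm difference. No section says so. That is a natural use of it, not a commitment. The plan's actual safeguard against contamination is randomizing by provider.
- **The primary result is safe from a common trend.** This also stands. A reader might infer that the primary comparison is biased by secular change. It is not, because both arms run concurrently.
- **The text speaks of analyses in the plural and names no model, so a time-series approach is not excluded.** True, but step 3 shows that three baseline months would not support one. It is also fair that no control-arm change at all would argue against both causes, if both act upward. The analysis is therefore not worthless, but it does not measure either component.
- **Outreach may cancel.** The described order is consent, baseline, randomization. If the baseline is collected after consent, the pre-trial outreach, consent-stage education and pre-study survey come before or during it and largely drop out of the change. If it is retrospective they do not, and the text does not settle which. The post-study survey comes too late to matter. It would overstate the case to list all of these as established causes. The periodic outreach to participating providers is the one that clearly extends past consent.

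**Conclusion.** The claim that this analysis can assess both contamination and secular trend should not stand. A control-only before/after change estimates their sum plus any effect of continuing outreach, and as specified it may not even be on the primary endpoint's scale. This follows from the design and needs no assumed rate.

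The size of the consequence is not known. In the 8% row, an all-contamination reading means that the trial understates the alert effect by 3.0 of 4.3 points (70%). That figure rests entirely on the assumed 8%, on additivity and on the 5% start, so it shows what the analysis could fail to distinguish and does not estimate bias.

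The matter is worth correcting before analysis, but it concerns interpretation. The randomized comparison stays valid as a comparison of the two arms as they were run.

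**What to change.** (a) Restate the Research Plan sentence: the control-group analysis describes the total change in the control arm and does not separate contamination from trend. Compute it with the 90-day intensification definition in both periods. Baseline visits need a 90-day window that closes before alerts begin, so the record extract must reach back further than three months.

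(b) Add a supportive contamination analysis. Among control providers, regress the change in intensification on the share of enrolled colleagues in the same practice who are in the alert arm, conditioning on the number of enrolled colleagues. Given that number, the share is set by randomization and should not depend on trend or outreach.

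(c) Optionally, describe the concurrent trend in non-enrolled providers from practices with no alert-arm provider. State that a difference-in-differences against them assumes a shared trend and still mixes contamination with outreach and study-awareness effects (C + O in step 2). It does not isolate contamination.

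**Costs.** (a) is wording and a wider extract. (b) uses mostly data that the trial already collects, plus a coded practice identifier. That must be squared with the commitments under Engaging Providers and Consent Waiver not to link clinicians to outcomes. Its power is likely to be low. Assume 25 trial and 25 × 3/9 = 8.3 baseline patients per control provider, rates of 5% and 8%, ICC 0.05 with a stable provider effect, and a share SD of 0.25 (the documents give no practice sizes):

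- SD of a provider's change = √(0.95 × [0.05 × 0.95/8.3 + 0.08 × 0.92/25]) = 9.1 points.
- Slope SE = 9.1 / (√50 × 0.25) = 5.1 points per unit share.
- Contamination averaging 3 points at a mean share of 0.5 is a slope of 6. Power is then about 22%, or 11% to 37% for a share SD of 0.15 to 0.35.

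A null result from (b) would therefore not rule out contamination, and the plan should say so. (c) uses non-randomized comparators. It also needs the eligibility trigger reconstructed, since the alert build runs only when an enrolled provider opens order entry.
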